Hepatic Steatosis Snap Shot

Sites Participating: All sites

Principal Investigator: [name] (University of Michigan)

Co-Investigators: [name]; [name]; [name];
[name]

Study Name: HEPATIC STEATOSIS IN CHRONIC HEPATITIS C: RISK FACTORS AND ROLE ON THE DEVELOPMENT OF HEPATIC FIBROSIS

Separate Consent Form: No

Withdrawal Form: No

Eligible Patients: Lead-in, Randomized, W20 Responders, Sustained Virologic responders and Breakthrough/Relapser
(Express patients are not eligible)

Visit Schedule (additional data/specimen and forms for AS)

Note: "X" means all participating sites take part.

Lead-In Phase

Visit Number →	Form #	S00	W00	W02	W04	W08	W12	W16	W20	W24
Fasting Insulin seq.121	Excel file		X							
Glycosylated Hemoglobin	121	X								

Randomized Phase

Visit Number →	Form #	R00	M12	M18	M24	M30	M36	M42	M48	M54
Fasting Insulin seq. 121	Excel file				X					
Glycosylated Hemoglobin	121									

Hepatic Steatosis in Chronic Hepatitis C: Risk factors and role in the development of hepatic fibrosis

Principal Investigator: [name]

Co-Investigators: [name], [name], [name], [name]

SPECIFIC AIMS:

The central hypothesis of this ancillary study is that hepatic steatosis plays a key role in the development of fibrosis and cirrhosis in patients with chronic hepatitis C. In addition, we hypothesize that both viral and non-viral factors are involved in the development of hepatic steatosis in patients with chronic hepatitis C, and the benefits of long-term interferon therapy is in part mediated via reduction of hepatic steatosis. The specific aims of this study are:

1. To determine the prevalence of hepatic steatosis in patients with chronic hepatitis C.
2. To determine if there is a correlation between hepatic steatosis and hepatic fibrosis in patients with chronic hepatitis C.
3. To identify viral and non-viral risk factors for hepatic steatosis in patients with chronic hepatitis C.
4. To identify metabolic predictors of week 20 and sustained virologic response
5. To determine the effects of long-term interferon therapy on hepatic steatosis in patients with chronic hepatitis C.
6. To determine the effects of virologic clearance on insulin resistance in patients with chronic hepatitis C.

RELATIONSHIP OF PROPOSED STUDY TO NIH HALT-C TRIAL

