The objective of the HALT-C trial is to determine if long-term interferon therapy can reduce the risk of progression to cirrhosis, decompensated liver disease and/or hepatocellular carcinoma (HCC) in patients with chronic hepatitis C who failed to respond to previous interferon therapy. The main goal of this ancillary study is to determine if hepatic steatosis plays a role in the development of fibrosis and cirrhosis in patients with chronic hepatitis C. This study will also examine risk factors for hepatic steatosis in patients with chronic hepatitis C. This ancillary study will help to improve our understanding of the mechanisms of hepatic fibrogenesis in patients with chronic hepatitis C and is therefore directly linked to the objective of the HALT-C trial. Most of the work involved in this study is related to the main protocol. The only additional elements involve simple clinical assessments such as waist circumference, one time testing for fasting insulin level, and grading of liver biopsies for hepatic steatosis. The latter component will be performed when liver biopsy slides (H&E) are graded for hepatic inflammation.

BACKGROUND AND SIGNIFICANCE

Macrovesicular steatosis is one of the characteristic histologic features of chronic hepatitis C. Hepatic steatosis has been reported in 31-72% patients with chronic hepatitis C [1-4], the wide range in prevalence being related to differences in patient selection in particular alcohol consumption, and the lack of standardization of grading systems for steatosis.

Steatosis is a well-recognized feature of alcoholic liver disease and non-alcoholic steatohepatitis (NASH) [5]. Non-alcoholic fatty liver disease (NAFL) which includes steatosis, steatohepatitis, and cirrhosis is now considered to be the most prevalent form of liver disease in the United States [6]. The

etiology of NASH is unknown, but it is frequently found in association with female gender, obesity, diabetes mellitus and hypertriglyceridemia [7,8]. Recent studies however, found that a significant proportion of patients with NASH do not have any identifiable risk factors [9,10]. These data suggest that other as yet unknown risk factors may be involved in NASH.

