This ancillary study will examine the prevalence and severity of hepatic steatosis in a large cohort of patients with chronic hepatitis C. Viral and non-viral risk factors for hepatic steatosis will be assessed prospectively. Hepatic steatosis will be graded using a standardized scoring system and will be correlated to semi-quantitative (Ishak) and quantitative (morphometry) assessment of hepatic fibrosis. The effects of interferon therapy on hepatic steatosis will also be determined. The advantages of utilizing the HALT-C trial for our proposed ancillary study include the large sample size, long duration of follow-up and the inclusion of an untreated control group. Because this is a prospective study, alcohol consumption can be more reliably assessed. Detailed and accurate quantification of past and current alcohol consumption is a major focus of the HALT-C trial. Life-time and ongoing alcohol consumption will be determined using the Skinner survey. Other risk factors that have not been examined in previous studies such as fat distribution and hyperinsulinemia will be evaluated. This trial will enable us to examine the prevalence and impact of hepatic steatosis in patients with chronic hepatitis C both cross-sectionally and longitudinally. The longitudinal part of the study will allow us to determine if hepatic steatosis in patients with hepatitis C fluctuate over time and to identify factors that correlate with these changes. It will also determine if changes in hepatic steatosis correlate with changes in hepatic fibrosis further supporting a role of hepatic steatosis in fibrogenesis. Long-term interferon therapy can potentially decrease steatosis by inducing weight loss or increase steatosis by elevating serum triglyceride level. This study will determine the net effects of long-term interferon therapy on hepatic steatosis in patients with chronic hepatitis C.

MATERIALS AND METHODS

Inclusion/Exclusion:

All Lead-in patients enrolled in the NIH HALT-C trial will be studied. This study will enroll approximately 1000 patients with chronic hepatitis C who have significant fibrosis (Ishak score of 3-6). Patients with other causes of liver disease will be excluded from this study. Express patients are not eligible for the Steatosis Ancillary Study.

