Patients will receive 6 months of combination therapy of interferon and ribavirin during the lead-in phase. Patients who remain viremic at treatment week 20 will be eligible for continued participation in this trial. These patients will be randomized to continue treatment with interferon alone for 3.5 years or no treatment. All patients will have repeat liver biopsies at the end of years 2 and 4.

This ancillary study will consist of a **cross-sectional** and a **longitudinal part**. In the following pages:

◆ Indicates additional data/sample collection for this ancillary study.

Schedule of Visits and Specimen Collection:

Cross-sectional Study – All tests performed at Screening (S00) or Baseline (W00).

This study will include all patients who remain eligible for continued participation in the NIH HALT-C trial after the lead-in phase. Baseline clinical data will be collected for all enrolled patients. Tests for insulin level and grading of liver biopsies for hepatic steatosis will not be performed until all patients have completed the lead-in phase to determine who will remain in the trial.

During the screening phase, clinical data will be collected and blood tests will be performed as part of the main protocol. Fasting blood glucose and triglyceride levels will be checked. Patients with known diabetes will be tested for glycosylated hemoglobin (HbA1c). These procedures are part of standard care of hepatitis C patients evaluated for interferon treatment and will be performed as part of the main protocol. An additional sample of blood will be collected for insulin level. Baseline liver biopsies will be scored for inflammation, fibrosis and iron. These assessments will be performed as part of the main protocol. The biopsies will additionally be graded for hepatic steatosis.

Baseline clinical data will be collected during the screenings or at baseline on:

- a) Sex, age, ethnicity, Form #1, Trial ID Assignment.
- b) Total body fat estimated by body mass index (BMI). BMI will be derived from body height and weight, Form #11, Physical Exam.
- c) ♦ Visceral fat estimated by waist circumference taken with a cloth tape at the level of the umbilicus, with the patient supine, Form #11, Physical Exam (See Appendix A for directions).
- d) Quantitative lifetime alcohol consumption and alcohol consumption during the year prior to entry into the Trial based on Skinner survey, Form #41.

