- e) ♦ History of diabetes, Form #3, Screening Medical History Interview. Current use of diabetic medications, Form #3, Screening Medical History Interview, and Form # 7, Baseline Medications Interview.
- f) History of hyperlipidemia, Form #3, Screening Medical History Interview. Current use of lipid lowering medications, Form #3, Screening Medical History Interview, and Form #7, Baseline Medications Interview.
- g) ♦ History of morbid obesity, Form #3, Screening Medical History Interview and Form #146, Weight History. Previous treatment for obesity such as jejunoileal bypass, Form #3, Screening Medical History Interview.
- h) ♦ Concomitant medications that may induce hepatic steatosis, Form #7, Baseline Medications Interview.

Laboratory tests during the screening phase (S00):

- a) Liver panel including AST and ALT, Form #35, Screening Visit 2 Local Lab.
- b) HCV genotype, Form #33, Central Lab - HCV Genotype.
- c) HCV RNA level, Form #31, Central Lab – HCV RNA.

- d) Serum iron/TIBC, Form #30, Local Lab.
- e) ♦ Fasting blood glucose, Form #30, Local Lab, and HbA1c for known diabetics, Form #121, Glycosylated Hemoglobin.
- f) Fasting triglyceride, Form #30, Local Lab.
- g) ♦ Fasting insulin level during the baseline visit (W00). Fasting insulin level will be tested at the Michigan Diabetes Center. Fasting insulin results will be sent to NERI as an excel file.

Baseline liver biopsies will be assessed by the central Pathology Committee for:

- a) Hepatic inflammation according to Ishak score.
- b) Hepatic fibrosis according to Ishack score as well as computerized morphometry after staining with sirrus red.
- c) Hepatic iron content according to the method determined by the Pathology Committee.
- d) ♦ Hepatic steatosis – the same H&E slide used for grading hepatic inflammation will be used to quantify hepatic steatosis. Hepatic steatosis will be scored based on percent of hepatocytes with fat. Scores will range from 0 to 4+: 0 (none), 1+ (1-5%), 2+ (5-33%), 3+ (33-67%), and 4+ (>67%).

Longitudinal study: This study will include all patients who completed the trial and have repeat liver biopsies at the end of years 2 and 4.

Serial clinical data will be collected on:

- a) Body weight at each visit, Form #11, Physical Exam. This will permit changes in total body fat or BMI to be determined.
- b) ♦ Waist circumference will be determined at the end of year 2 (M24) and 4 (M48) to assess changes in visceral fat, Form #11, Physical Exam.

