 - Alcohol consumption: life time alcohol consumption and consumption within the year prior to the liver biopsy.
 - Viral factors: HCV genotype, HCV RNA level.
 - Hepatic inflammation: ALT level and hepatic inflammation grade.
 - Iron: serum iron, TIBC and hepatic iron score.

Risk factor data such as BMI, life time alcohol consumption, diabetes status etc. will be coded as categorical or continuous variables as appropriate. These will be evaluated against the degree of steatosis (5 levels) and dichotomous collapsed steatosis codes (such as <33% vs \geq 33%) using the Cochran-Mantel-Haenszel chi-square test with one degree of freedom. Multivariate analysis will be performed using logistic regression analysis. These risk factor variables and the steatosis levels will similarly be evaluated against the fibrosis scores (6 levels). Because fibrosis will also be quantified morphometrically, it will also be analyzed as a dependent variable by analysis of variance.

4. These risk factors and their relationship to week 20 and sustained virologic response will also be assessed.

Univariate analysis will be carried out using categorical or continuous variables as appropriate. These will be categorized against dichotomous (W20 responder v nonresponder, SVR v no SVR (all W20 nonresponders will be categorized as no SVR)) variables using the Cochran-Mantel-Haenszel chi-square test with one degree of freedom. Multivariate analysis will be performed on significant variables identified in univariate analysis by logistic regression.

Longitudinal study

The following analyses will be performed:

1. Prevalence of hepatic steatosis in year 4 biopsies will be compared to the year 2 and baseline biopsies of all patients and separately for the treated patients and controls.
2. Changes in hepatic steatosis between year 4 and baseline biopsies will be compared for the entire cohort of patients, and separately for the treated patients and controls.
3. Correlation between changes in hepatic steatosis with changes in hepatic fibrosis.
4. Correlation between changes in hepatic steatosis and changes in other risk factors for hepatic steatosis such as BMI, alcohol consumption, triglyceride level, hepatic inflammation, and hepatic iron content.
5. Correlation between changes in insulin resistance (measured using the homeostasis model assessment (HOMA)) from baseline to week 60 of the lead-in patients and virologic response or relapse.

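### The longitudinal analysis set is chosen after randomization (completers with year-2 and year-4 biopsies), which conflicts with the plan's references to all patients and leaves Aim 5 open to selection bias

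*Combined protocol and SAP*

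**What the plan says.** The Longitudinal study paragraph under Schedule of Visits and Specimen Collection sets the inclusion rule: "This study will include all patients who completed the trial and have repeat liver biopsies at the end of years 2 and 4".

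The opening of Materials and Methods describes the randomization: "These patients will be randomized to continue treatment with interferon alone for 3.5 years or no treatment". It then gives the biopsy schedule: "All patients will have repeat liver biopsies at the end of years 2 and 4".

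Aim 5 is a treatment-effect question: "To determine the effects of long-term interferon therapy on hepatic steatosis in patients with chronic hepatitis C". The Background counts among the advantages of using the parent trial its "long duration of follow-up and the inclusion of an untreated control group".

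The introduction to Data Analyses says that all patients qualifying to continue after the lead-in phase are included, and gives the unknown effect of interferon on steatosis as a reason for the larger sample. In the longitudinal list, item 1 compares year-4 prevalence with year 2 and baseline for all patients and by arm. Item 2 reads: "Changes in hepatic steatosis between year 4 and baseline biopsies will be compared for the entire cohort of patients, and separately for the treated patients", with the control arm as the other separate group. Item 3 correlates change in steatosis with change in fibrosis. The plan names no between-arm test and no missing-data method.

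**The concern.** Completing the trial, having a year-2 biopsy and having a year-4 biopsy are all determined after randomization. One arm receives interferon for 3.5 years and the other receives nothing, so reasons for leaving could differ between arms. Once membership of the analysis set depends on such events, randomization no longer guarantees that the two groups are comparable. The untreated control group then loses much of the value the Background claims for it.

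Two further consequences do not depend on a difference between arms. Patients who die or leave early cannot have completed the trial. If they differ in steatosis or fibrosis, within-arm prevalence and the steatosis–fibrosis change correlation describe a selected group. Requiring both follow-up biopsies also discards data that the analyses could use: item 2 needs only baseline and year 4, yet a patient with those two biopsies and no year-2 biopsy is dropped.

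**Working it through.** **1. Who is included.** The sections give two accounts.

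- Longitudinal study paragraph: trial completers with biopsies at years 2 and 4.
- Materials and Methods, Data Analyses introduction, and longitudinal item 1: all patients.

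The biopsy schedule is an intention, not a rule for a biopsy that is not obtained. The all-patients statements do not say what to do when one is missing. Only the completer rule could be applied as written.

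**2. Inputs for an illustration.** The documents give no sample size calculation, completion rate or dropout rate for the longitudinal part, so there is no planned figure to reproduce. Data Analyses says the study will have 3–4 times the patients of a published series of 148: 3 × 148 = 444 and 4 × 148 = 592. These are assumptions: 1:1 allocation (the ratio is not stated), a 40% year-4 prevalence p of some steatosis category in both arms (no true effect), and all loss rates.

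**3. Formulae.** Let m1 and m0 be the loss rates among patients with and without the category. Prevalence among completers is

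p(1 − m1) / [p(1 − m1) + (1 − p)(1 − m0)].

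Bias is the treated value minus the control value. For a two-sided 5% test of two proportions with pooled standard error s0 and unpooled standard error s1, the false-positive rate is Φ[(d − 1.96·s0)/s1] + Φ[(−d − 1.96·s0)/s1], where d is the bias.

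**4. Results.**

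| Case | Treated m1 / m0 | Control m1 / m0 | Completer prevalence, treated / control | Bias (points) | False positives (444–592 randomized) |
|---|---|---|---|---|---|
| a | 20% / 20% | 20% / 20% | 40.0% / 40.0% | 0 | 5% |
| b | 30% / 15% | 30% / 15% | 35.4% / 35.4% | 0 | 5% |
| c | 20% / 15% | 30% / 15% | 38.6% / 35.4% | 3.1 | 9–11% |
| d | 15% / 15% | 40% / 15% | 40.0% / 32.0% | 8.0 | 35–44% |
| e | 15% / 30% | 30% / 15% | 44.7% / 35.4% | 9.3 | 42–53% |

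Case c in full, with 592 randomized (296 per arm):

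- Treated: 0.4 × 0.80 = 0.32 and 0.6 × 0.85 = 0.51, so 0.32/0.83 = 0.3855 with 296 × 0.83 = 245.7 completers.
- Control: 0.4 × 0.70 = 0.28, so 0.28/0.79 = 0.3544 with 296 × 0.79 = 233.8 completers.
- d = 0.0311, s0 = 0.0441 and s1 = 0.0441. The two tails are 0.1046 and 0.0038, total 0.108.

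In case b the arms agree, but prevalence in each falls from 40% to 35.4%.

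**5. Bounds without assuming a pattern.** If a share m is missing in each arm, the difference for all randomized patients lies within (1 − m) × observed difference ± m. With an observed difference of zero, that is ±10, ±20 or ±30 points at 10%, 20% or 30% missing.

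**6. Data discarded.** Suppose 10% miss year 2 and 20% miss year 4, independently (assumed).

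- Both biopsies: 0.9 × 0.8 = 72%, or 320 to 426 of 444 to 592.
- Year 4 alone, which is all item 2 needs: 80%, or 355 to 474.
- At least one follow-up biopsy: 1 − 0.1 × 0.2 = 98%.

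On these rates, requiring year 2 as well costs item 2 eight percentage points of the cohort (0.80 − 0.72), about 36 to 47 patients.

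**The case against.** The strongest reply is that the completer sentence may be loose drafting. The schedule plans both biopsies for everyone, Data Analyses says all patients are included, and the M24 and M48 biopsies are to be graded with no completer condition. That stands as evidence that the plan is unreconciled rather than settled. It does not supply a rule for a missing biopsy.

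A reader might infer that the set removes patients whose disease progressed, since the parent trial's objective names cirrhosis, decompensation and hepatocellular carcinoma. The documents do not support that. They nowhere say that decompensation or cancer ends participation or biopsies, and they give no event rates. Fibrosis progression is read on the repeat biopsies, so a progressor who completes the trial and is biopsied at both visits stays in. Only death and early departure follow from the completion condition.

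A reader might also infer that the arm comparison is certainly biased. Cases a and b show otherwise. If sicker patients leave in the same pattern in both arms, the arm difference under no true effect is still zero. The large figures need loss to differ by arm in its relation to outcome, and case e needs opposite directions, for which the documents offer no evidence. The false-positive rates also belong to a between-arm test that the plan does not specify.

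**Conclusion.** The concern holds as an exposure, not as a demonstrated bias. The stated set is defined by events after randomization, the other sections contradict it, and no missing-data method offsets it. With no true arm effect, the bias in the arm comparison is zero if loss is unrelated to outcome or depends on outcome identically in both arms. It can reach several prevalence points if loss depends on both arm and outcome. The 3.1 to 9.3 points and the 9% to 53% false-positive rates are illustrative; they rest on the assumed 40% prevalence, 1:1 allocation and invented loss rates.

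Outcome-related loss can distort within-arm prevalence and the steatosis–fibrosis change correlation even when the arms lose patients alike, so these results may under-represent patients who progressed. The loss of usable biopsies is certain wherever a patient misses one visit; its extent is unknown. This should be corrected before the longitudinal analysis.

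**What to change.** - Reconcile the Longitudinal study paragraph with Materials and Methods and with Data Analyses. For the biopsy analyses (longitudinal items 1–4), define the population as all randomized lead-in patients with a baseline biopsy. Requiring at least one follow-up biopsy for entry would itself be a post-randomization condition.
- For Aim 5, state an explicit comparison by assigned arm, using every available biopsy (baseline, M24, M48) in a likelihood-based mixed or ordinal repeated-measures model.
- Report missing biopsies by arm, visit and reason.
- Add a sensitivity analysis for informative loss that treats death explicitly.
- Keep the completer set as a supportive analysis.

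The cost is revised analysis wording and somewhat more modelling; no new visits or samples are needed. The model relies on loss being missing at random given the observed data. It corrects for loss explained by an observed year-2 biopsy, but not for loss driven by later, unobserved disease. Checking the model on data whose loss is generated from observed year-2 steatosis would succeed by construction, so the sensitivity analysis is a necessary part of the change.

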- c) Quantitative alcohol consumption during the study will be assessed every 6 months, Form #42, Alcohol Use Questionnaire.
- d) ♦ New diagnosis of diabetes, and/or hyperlipidemia during the study, Form #30, Local Lab, and Form #10, Study Visit.
- e) ♦ Concomitant medications that may induce hepatic steatosis, Form #12, Medications Interview.

Serial laboratory tests will be performed per protocol:

- a) Liver panel at each visit, Form #30, Local Lab.
- b) HCV RNA every 3 months, Form #31, Central Lab – HCV RNA.
- c) Fasting blood glucose every 6 months, Form #30, Local Lab.
- d) Fasting triglyceride level every 6 moths, Form #30, Local Lab.
- e) ♦ Fasting insulin level at the end of year 2 (M24) Excel file, with Fasting Insulin results.

Liver biopsies obtained at the end of year 2 (M24) and year 4 (M48) will be assessed for hepatic inflammation, fibrosis, iron and steatosis.

To address aim 6, all non-diabetic patients with TW 20 response followed until TW 60 will be included. A group of matched (BMI, race, HCV genotype) non-diabetic controls with no virologic response at TW20 will also be studied if a difference in IR is detected at TW 60 between patients with SVR and relapsers.

1. Serial clinical data at baseline, TW20, TW 48, and TW 60 for patients with TW20 virologic response, and data at baseline and TW20 for matched controls.
2. Serial laboratory tests: liver panel, HCV RNA, glucose, triglycerides as per protocol. Fasting insulin levels at TW00 and TW 60 for patients with TW20 response.

If results show a difference in IR at TW60 between patients with SVR and relapsers, fasting insulin levels at TW20 will also be tested in study subjects and matched controls.

Specimen Collection, Handling, and Shipping:

- **Blood collection and processing for insulin assays at baseline and at year 2 (M24)**

1. Collect blood in a red top tube – 7mls (Do NOT use tubes that have EDTA coating).
2. Allow the blood to clot for at least 30 minutes – this does not necessarily have to be on ice if not available (blood can be allowed to clot for up to 2-2.5 hours).
3. Spin the tube for 10-15 minutes at 3000 RPMs.

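### The baseline-to-year-4 change in alcohol intake crosses two forms whose comparability the plan does not establish, so its correlation with change in steatosis should be adjusted for baseline and checked within one form

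*Combined protocol and SAP*

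**What the plan says.** All references are to the combined protocol and SAP.

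- **Baseline** (Materials and Methods, Cross-sectional Study, baseline clinical data, item d): "Quantitative lifetime alcohol consumption and alcohol consumption during the year prior to entry into the Trial based on Skinner survey, Form #41".
- **Follow-up** (Longitudinal study, serial clinical data, item c): "Quantitative alcohol consumption during the study will be assessed every 6 months, Form #42, Alcohol Use Questionnaire". The recall period and the items of Form #42 are not given.
- **Background and Significance**, last paragraph: "Life-time and ongoing alcohol consumption will be determined using the Skinner survey".
- **Data Analyses, Longitudinal study, item 4**: "Correlation between changes in hepatic steatosis and changes in other risk factors for hepatic steatosis such as BMI, alcohol consumption, triglyceride level", followed by hepatic inflammation and iron. The item does not say which baseline alcohol measure is used, which follow-up reports enter, how they are combined, or over which interval change is taken.
- **Data Analyses, Longitudinal study, item 2**, the only place that fixes an interval for steatosis change: "Changes in hepatic steatosis between year 4 and baseline biopsies will be compared for the entire cohort of patients".
- **Data Analyses, Cross-sectional study**, which describes the recent baseline window a little differently: "life time alcohol consumption and consumption within the year prior to the liver biopsy". Baseline item d counts back from trial entry instead.

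Form #42 is not listed at baseline, and Form #41 is not listed at follow-up.

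**The concern.** A change score is interpretable only if both ends are on the same scale. Here the two ends sit on differently numbered and named forms. One has a stated window of a year (besides lifetime intake); the other has no stated window and is given every six months. Weight, by contrast, is on Form #11 throughout, so change in BMI does not have this problem.

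Two consequences are possible.

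- **False association.** If Form #42 picks up proportionally less drinking than Form #41, a patient whose drinking has not changed shows an apparent fall, and the fall is larger for heavier drinkers. The change score then carries baseline drinking. If steatosis change also depends on baseline steatosis, and baseline steatosis is related to drinking, the two change scores correlate although nobody's drinking changed.
- **Dilution.** Person-to-person disagreement between the forms adds noise and weakens a true correlation.

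This matters because the Background treats alcohol as a plausible cause of steatosis in these patients and presents careful alcohol measurement as a strength of the cohort.

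**Working it through.** The plan gives no power, sample-size or effect figure for the alcohol-change analysis, so there is nothing of its own to reproduce. The check sets the text side by side, then works through the algebra and a simulation on stated assumptions.

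**1. The text**

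| Point in time | Form | Instrument named there | Window |
|---|---|---|---|
| Baseline | #41 | Skinner survey | lifetime; year before entry |
| On study, every 6 months | #42 | Alcohol Use Questionnaire | not stated |
| Ongoing intake, per Background | none named | Skinner survey | not stated |

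A change of form is documented. A change of instrument is not, because the Background names the Skinner survey for ongoing intake too. A change of recall window could be guessed from the six-month frequency but is not stated.

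**2. When a difference between forms matters**

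Let A be true intake, the same at both times, and let S0 be baseline steatosis.

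- *Constant offset c.* Observed change = (A + c) − A = c for every patient. It shifts the mean change but leaves a correlation untouched.
- *Proportional capture f.* Observed change = fA − A = (f − 1)A. At f = 0.7 this is −0.3A, so the score is baseline drinking with the sign reversed.
- *Steatosis change that depends on its baseline:* ΔS = −b·S0 + noise. Then cov(observed alcohol change, ΔS) = (f − 1)(−b)·cov(A, S0) = (1 − f)·b·cov(A, S0).

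The product is zero if f = 1, if b = 0, or if baseline drinking and steatosis are unrelated. With f < 1, b > 0 and a positive baseline relation it is positive, which would read as less drinking going with less steatosis.

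**3. Size, by simulation**

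Assumptions: N = 500; stable, lognormal intake; 30% reporting error on each form; baseline alcohol–steatosis correlation 0.2 to 0.3; Spearman test of change against change at nominal 5%. The value of N is consistent with the plan's statement of 3–4 times 148 patients (3 × 148 = 444; 4 × 148 = 592). The other values are not in the documents.

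| Analysis | f = 0.8 | f = 0.5 |
|---|---|---|
| Baseline to year 4, unadjusted, steatosis falls in proportion to baseline | 9–13% | 21–40% |
| Same, no dependence on baseline steatosis | near 5% | near 5% |
| Adjusted for baseline intake and baseline steatosis | 4–7% | 4–7% |
| M24 to M48, Form #42 at both ends, unadjusted | about 3–7% | about 3–7% |

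At f = 1 the unadjusted rate is about 5–6%. The inflated figures move with the settings (strength of the decline, continuous or five-grade steatosis): across those tried they ran from 6–16% at f = 0.8 and from 18–66% at f = 0.5. The direction is stable; the exact size is not.

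**4. Dilution**

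Let k be the variance of the person-specific form difference divided by the variance of true change, with that difference independent of steatosis change. Observed correlation = true correlation × 1/√(1 + k).

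- k = 0.25: factor 0.89
- k = 0.5: factor 0.82
- k = 1: factor 0.71, so a true 0.20 becomes 0.20 × 0.71 = 0.14

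The documents give no value for k.

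**The case against.** The strongest reply is that a second form number is not a second instrument. The Background says that ongoing intake also comes from the Skinner survey, and a follow-up version would naturally omit the lifetime items and could carry another title. Neither alcohol item bears the mark for data added by this ancillary study, so both forms appear to belong to the main trial, whose documents are not available here. This stands. A reader might infer that the plan switches instrument and recall window after baseline; the documents do not establish either.

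The reply continues that inflation needs two undocumented conditions at once, proportional under-capture and steatosis change that depends on its baseline. That also stands. The second condition is not far-fetched on a bounded 0-to-4 grade, where grade 0 cannot improve and grade 4 cannot worsen, but the plan does not state it.

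Thirdly, alcohol is one of five examples in one exploratory correlation, no specific aim names change in alcohol, and the baseline cross-sectional analyses use Form #41 throughout. This limits the weight of the point.

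Finally, a reader might conclude that M24-to-M48 should become the main alcohol analysis. That does not follow. It would halve the interval, drop the lead-in and the first part of the randomized phase, and separate alcohol from the baseline-to-year-4 steatosis change, although covariate adjustment already controls the false-positive rate.

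What the reply does not remove is that the two descriptions of ongoing intake remain unreconciled and the alcohol change score is undefined even if the forms share their items.

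**Conclusion.** The point holds as a risk to one secondary analysis, not as a demonstrated bias. It is documented that the baseline-to-year-4 alcohol change crosses two forms, that the text leaves open whether they are the same instrument over the same window, and that longitudinal item 4 does not define the change score.

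If Form #42 captures proportionally less and steatosis change depends on its baseline level, an unadjusted change-on-change correlation can be spurious, with a false-positive rate of roughly 9–13% at 80% capture and 21–40% at 50% under the settings above. If either condition fails, the rate stays near 5%, and a constant offset cancels. Dilution of a true correlation is possible in addition, by an amount that the documents do not allow one to fix. The cross-sectional alcohol analyses are unaffected.

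**What to change.** In Data Analyses, Longitudinal study, item 4:

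1. Keep the baseline-to-year-4 interval. Express alcohol as average intake per day on both forms, and name the baseline measure and the follow-up reports that enter the score. A common unit alone does not remove a proportional difference, so step 2 is also needed.
2. Adjust the steatosis–alcohol change analysis for baseline alcohol intake and baseline steatosis grade.
3. Add the M24-to-M48 change, with Form #42 at both ends and the M24 and M48 biopsies, as a same-form sensitivity analysis. It also avoids the between-form noise that adjustment does not remove.

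In the text, reconcile the Background with serial clinical data item c: state which instrument measures ongoing intake, whether Form #42 uses the Skinner items, and what period it covers. Align the two descriptions of the baseline year (before entry, before biopsy) at the same time.

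Cost: wording and slightly more analysis work, on data already scheduled for collection. The sensitivity analysis covers only 2 years, so it has less true change to work with and should not be read as a replacement for the main result.
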